1.3 Exploratory Objectives

To determine the immune correlates of the clinical activity of MK-3475

The endpoints will include immunohistochemical (IHC) and gene expression analysis, whole exome sequencing, and neoantigen identification focusing on delineating the immune components and immunologic milieu within the tumor before therapy. The IHC analytes will include, but are not limited to Merkel cell polyomavirus (MCPyV) tumor antigen (T-Ag), programmed cell death 1 (PD-1), and its ligand 1 (PD-L1), CD8, CD3, CD68, CD45, and CD56. In addition, MCPyV viral DNA will be quantified in the tumor and T cell receptor sequencing in tumor infiltrating lymphocytes (TIL) will be performed where pre- and post-treatment biopsies

are available. Cellular and humoral MCPyV-specific immune responses will be assessed with Enzyme-Linked ImmunoSpot (ELISpot) serology assays in blood samples at baseline, after initiating MK-3475 therapy, and correlated with clinical responses over time. Among patients with corresponding major histocompatibility complex (MHC)-peptide tetramers, pre-and post-treatment samples of circulating MCPyV-specific CD8 T cells will be isolated by flow cytometry and subjected to deep immunophenotyping by messenger RNA (mRNA) expression analysis.

Hypothesis: MK-3475 will enhance functional activity of MCC-specific lymphocytes and facilitate tumor regression. Thus, the clinical endpoints associated with tumor regression and durability of response will be correlated with the pretreatment levels and type of immune cell infiltration in the tumor, PD-1 and PD-L1 expression and association in the tumor, or systemic measures of immune response to tumor-specific viral MCPyV antigens.

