2.5 Correlative Studies Background

The links between the immune system and MCC are particularly strong due to the frequent presence of the MCPyV and the documented improved survival of MCC patients based on T-cell immune function. It is therefore plausible that MK-3475 responses will correlate with the nature of the immune response in the tumor microenvironment including PD-L1 expression. In addition, there are several unique aspects of the correlative studies proposed for this trial. These include the ability to study MCPyV-specific T cells (in a subset of patients with corresponding MHC-peptide tetramers) in terms of their number, functional status, and surface receptor phenotype and gene expression profile. These correlative studies will attempt to address the following questions:

- 1) Are MCPyV-positive tumors more likely to respond to PD-1?
- 2) Does the MCPyV DNA copy number or extent of viral protein expression by IHC predict responsiveness?
- 3) Is intratumoral CD8 T-cell infiltration a marker for patients that will respond to MK-3475?
- 4) Are patients with antibodies to the MCPyV oncoprotein more likely to respond to MK-3475?
- 5) Do antibody titers to the viral oncoprotein provide greater or different insights into responses than gold-standard imaging studies?
- 6) Do responsive patients (as compared to non-responders) demonstrate changes in cell surface exhaustion parameters (PD-1/TIM-3) for virus-specific T cells?
- 7) Are virus-specific or neoantigen-specific T cells more active following PD-1 therapy? (as assessed by interferon and other cytokine production after peptide stimulation and assay by ELISpot and/or intracellular cytokine analysis)
- 8) What immune evasion mechanisms are active in tumors that fail to respond to MK-3475? (Biopsies will be carried out when feasible, on accessible tumor sites.)
- 9) How does the mutanome landscape of MCPyV-positive patients compare to that of MCPyV-negative patients? How does mutational load rank within the NIH Cancer Genome Atlas (TCGA)?
- 10) How does predicted immunogenicity of neoantigens differ between MCPyVpos and MCPyVneg tumors? Does this difference correlate with response to pembrolizumab?
- 11) How does the T cell response to either viral antigens or neoantigens change over the course of treatment with pembrolizumab?

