- 12) What is the phenotype of neoantigen-reactive or virus-reactive T cells and how does this phenotype change over the course of pembrolizumab therapy? Does a particular phenotype correlate with response?

2.5.1 *Evaluation of Tumor Biopsies for Immune Cell Infiltrate—Laboratory Correlative Study #1*

All patients recruited in the study must have an available archival tumor biopsy for biomarker analyses. If sufficient archival tumor tissue (at least 0.5 × 0.5 × 0.5 cm) collected before MK-3475 therapy is not available, a baseline biopsy will be obtained before enrolling in the study, assuming this can be carried out safely. Because tumor-infiltrating immune cells are associated with clinical outcome in MCC tumors, infiltrates derived from pre-therapy tumor tissue and from optional biopsies of responding, stable or progressing lesions in patients who have not achieved CR will be assessed by IHC to determine extent and the nature of the T-cell infiltration and the immune milieu of the tumor microenvironment. PD-L1 is a critical ligand for PD-1 and may be associated with response to MK-3475, hence, PD-L1 expression will be quantitated in the baseline formalin-fixed paraffin-embedded tumor specimens from all cases at a Merck-designated contract research organization (CRO). The following cellular markers will also be analyzed by IHC analyses in this study: CD3, CD8, PD-1, MHC Class 1, and anti-MCPyV T-Ag.

Additionally, with a view to further characterize the immune cell infiltrate (pending discussions between investigators and Merck in light of study results and current literature), tumors may also be assayed by IHC for a variety of other markers including CD4 (T cells), CD56 and CD16 (NK and NK T cells—because many MCC tumors are CD56-positive themselves, CD16 is an important additional marker), CD45 (leukocytes), CD19 (B cells), CD68, glucocorticoid-induced tumor necrosis factor receptor family-related gene (GITR), TIM-3, forkhead box P3 (FOXP3), and lymphocyte-activation gene 3 (LAG3). Tumor tissue may also be tested for gene expression (NanoString Technologies).

In patients who have not achieved CR (either responding, stable or progressing lesions) a biopsy sample of a tumor may be obtained if feasible and safe (core, punch or excisional biopsy). This biopsy is highly preferred, but optional. The biopsy will be analyzed as outlined above. All studies indicated above maybe carried out for the biopsy.

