The majority of the IHC studies will be performed at the FHCRC Core/[name] Laboratory with oversight by [name] laboratory or at PhenoPath in Seattle, WA. Pre- and post-treatment levels of CD8+ T-cell tumor infiltrates will be assessed using criteria defined in Paulson, et al [[Paulson 2011](#)]. MCPyV protein expression in tumor tissue will also be assessed by IHC.

The DNA-PCR assay will be performed by [name] in a clinical grade virology laboratory (Vaccine and Infectious Disease Division at FHCRC).

PD-1 and PD-L1 expression will be tested by multiparametric IHC at Merck Research Laboratories in Palo Alto, CA, and PD-1 expression will also be tested with chromogenic IHC at a Merck-designated CRO. The multiparametric studies performed by Merck Research Laboratories will allow simultaneous determination of subcellular localization and identity of tumor/inflammatory cell types expressing PD-L1. When feasible, samples will also be assessed by [name] at Johns Hopkins using multi-spectral immunofluorescence as detailed in the NEJM manuscript [[[name] 2016](#)]. The option will be left open to subsequently assess further analytes by IHC at PhenoPath or other collaborators based on mutual agreement with the investigators/CITN and Merck.

mRNA expression (Nanostring) will be performed at Merck Research Laboratories in Palo Alto using unstained tissue slide material or may be performed at NanoString Technologies in Seattle, WA, pending mutual agreement on feasibility and logistics between NanoString Technologies & Investigators/CITN.

9.2.2 ***Merkel Cell Polyomavirus–Specific Cellular Immune Responses—Laboratory Correlative Studies #3–#5***

9.2.2.1 ***Collection of Specimen(s)***

Blood draws will be performed by venipuncture on study subjects just before, during, and at end of treatment. These blood draws will typically be carried out on the same visit as imaging scans.

9.2.2.2 ***Handling of Specimens(s)***

Yellow-top tubes (for subsequent PBMC isolation) will be shipped on day of blood draw for overnight delivery to the CITN Central Laboratory.

9.2.2.3 ***Shipping of Specimen(s)***

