PFS and OS by the following biomarker categories: 
 • pre-therapy CD8+ • pre-therapy CD3+ T-cell infiltration in tumor • pre-therapy PD-1 and PD-L1 expression in tumor, 
 • * pre-therapy immune response to MCPyV 	Descriptive statistics	Eligible subjects who receive at least 1 dose of treatment	censored at last assessment

ORR by the following biomarker categories:
 
 • pre-therapy CD8+ • pre-therapy CD3+ T-cell infiltration in tumor • pre-therapy PD-1 and PD-L1 expression in tumor, 
* pre-therapy immune response to MCPyV
	
Descriptive statistics
	
Eligible subjects who receive at least 1 dose of treatment
	
Missing value considered nonresponder

--	-------------------------------	---	--

Note: PD after 1 or more missed visits will be counted as PD as of the date of documented disease progression. An additional sensitivity analysis will be performed where subjects with 2 or more missed visits before progression will be censored at the last disease assessment before the ≥ 2 missed disease assessments.

13.5.2 *Statistical Methods for Safety Analyses*

Safety and tolerability will be assessed by clinical review of all relevant parameters including adverse experiences, laboratory tests, vital signs, and ECG measurements.

Adverse experiences will be summarized as counts and frequencies by toxicity grade. Summary statistics (median and range) for time to onset of first drug-related toxicity will be provided.

Laboratory assessments, vital signs, and other safety endpoints will be summarized using descriptive statistics as appropriate.

13.5.3 *Summaries of Baseline Characteristics, Demographics, and Other Analyses*

The number and percentage of subjects enrolled, and the primary reason for discontinuation will be displayed. Demographic variables (such as age) and baseline characteristics will be summarized either by descriptive statistics or categorical tables. No statistical hypothesis tests will be performed on these characteristics.

13.6 **Multiplicity**

The treatment comparison will be tested at one sided 5% alpha level and no multiplicity adjustment will be applied.

13.7 **Sample Size/Accrual Rate and Power Calculations**

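### The exploratory rows of Table 13.1 relate outcome to tumor and immune markers only by category, with no cut points, although the hypothesis concerns marker levels; a full-scale summary of the graded markers would use the data better

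*Combined protocol and SAP*

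**What the plan says.** Table 13.1 in Section 13.5 has two exploratory biomarker rows. One covers "PFS and OS by the following biomarker categories" and the other "ORR by the following biomarker categories". Both list pre-therapy CD8+, CD3+ T-cell infiltration, "pre-therapy PD-1 and PD-L1 expression in tumor" and pre-therapy immune response to MCPyV. The method in both rows is "Descriptive statistics". No cut point, number of groups, model or test is given for any marker. The opening of Section 13 says no separate SAP will be issued.

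The hypothesis behind these rows is in Section 1.3: tumor regression and durability of response "will be correlated with the pretreatment levels and type of immune cell infiltration in the tumor", or with PD-1 and PD-L1 expression, or with systemic immune response to the virus.

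On measurement scale, Section 2.5.1 says "PD-L1 expression will be quantitated in the baseline formalin-fixed paraffin-embedded tumor specimens". Section 9.2.1.4 says "Pre- and post-treatment levels of CD8+ T-cell tumor infiltrates will be assessed using criteria defined in" a cited publication, and the protocol does not reproduce that scale. For MCPyV antibody, Section 2.5.4 expects half of patients to be positive, repeats the assay only in those who are, and asks about both seropositivity and titer.

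**The concern.** The objective is about how much of a marker is present, while the only analysis rule sorts patients into groups. Once a graded marker is grouped, everyone on one side of the cut is treated as identical. With 50 patients, and perhaps a dozen responders, there is little information to spare.

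The cut is also left open. The trial is open-label (Section 13.1), and Section 2.4.1 shows that response results were known when enrollment was expanded. A cut chosen at analysis could therefore be influenced by outcomes, even unintentionally. A reader of the final report could not tell a pre-planned threshold from one picked because it separated the curves. What is at stake is how well the trial answers its immune-correlate question. The efficacy conclusion is not at stake.

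**Working it through.** **1. The plan's own figures.** The only power statement is for the primary Simon design: 9 then 24 patients, reject at 3 or more responses, 5% against 25%. The exact two-stage binomial gives power 0.903 and type I error 0.093, consistent with the stated 0.90 and 0.10. No power or precision figure exists for the biomarker rows, so nothing below contradicts a stated number.

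**2. Information kept by a split.** For a normally distributed marker cut so that a fraction q lies on one side, and a weak to moderate association, the information kept relative to the full scale is φ(z_q)² / [q(1−q)].

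- q = 0.50: 0.3989² / 0.25 = 0.637
- q = 0.25: 0.3178² / 0.1875 = 0.539
- q = 0.10: 0.342

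With n = 50, a median split leaves the equivalent of 50 × 0.637 ≈ 32 patients, and a 75/25 split leaves 50 × 0.539 ≈ 27. In terms of precision, relative error grows by 1/√0.637 ≈ 1.25 for a median split. This applies even when no test is done.

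**3. The same loss expressed as power (illustration).** Section 13.5 sets one-sided 0.05 for any test. If the full-scale analysis had 80% power, the noncentrality is 1.645 + 0.842 = 2.487. After a median split, Φ(2.487 × √0.637 − 1.645) = Φ(0.34) ≈ 0.63, a loss of about 17 points. At 30% full-scale power the same formula gives a loss of about 7 points.

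**4. Simulation at n = 50.** Assumptions: normal (log) marker, two-sided 5%, shift of 0.8 SD between responders and non-responders, median split.

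| ORR | Wilcoxon, full scale | Chi-square, median split | Difference |
|---|---|---|---|
| 25% | 0.63 | 0.48 | 15 points |
| 50% | 0.76 | 0.64 | 12 points |

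Over shifts of 0.6 to 1.0 SD and ORR of 25% to 50%, the difference is about 9 to 15 points, with simulation error of about a point. Other assumptions move it. A logistic model with an odds ratio of 1.5 per SD at ORR 50% loses only 4 points (two-sided 5%, median split). An odds ratio of 2 per SD at ORR 50% with a 75/25 split loses 24 (one-sided, 73.6% to 49.8%).

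**5. Effect of an open cut.** Take a marker unrelated to response, n = 50, and the best-looking cut anywhere in the inner 80% of ranks. A nominal two-sided 5% chi-square then flags an association in about 38% of trials at ORR 25% and 39% at ORR 50%. This is the worst case of unrestricted searching. The documents do not say anyone will do this, but they do not close it off.

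**6. Where categories are the better choice.** Suppose half of patients are undetectable and response depends only on being positive. With assumed response rates of 10% v 40%, chi-square on positive/negative has power 0.70 against 0.59 for Wilcoxon. With 30% v 70% it is 0.83 against 0.75. The direction reverses, and Section 2.5.4 makes this plausible for MCPyV serology.

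**The case against.** The strongest reply is that both rows are descriptive. The plan names no test, alpha or power target for them, so it has no power to lose. A reader might infer that this 50-patient trial forfeits a definite amount of power, say 11 to 30 points. The documents do not support that. Effect size, split, test and sidedness would all have to be assumed. The upper end of such a range comes from using Fisher's exact test: at 0.8 SD and ORR 25%, Fisher gives 0.33 where chi-square gives 0.48 on the same split. Much of that gap is Fisher's conservatism (null rejection about 0.03 or lower at a nominal 5%) and is not caused by categorising. This part of the reply stands, and any power figure should be read as illustration. It does not remove the loss of precision in step 2, which affects a descriptive table too.

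Second, the word categories could mean types of biomarker, with no cut intended. That is possible. The table would then say nothing about how the marker enters the analysis, and stating a full-scale summary would still be useful.

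Third, not every marker is shown to be continuous. The CD8 scale rests on a cited source and serology may be effectively binary. This stands and limits the fix. The Section 2.5 question "Does the MCPyV DNA copy number or extent of viral protein expression by IHC predict responsiveness" shows interest in degree, but neither DNA copy number nor viral protein expression appears in the two biomarker rows. It is not evidence that the plan categorises them.

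Fourth, level-based analysis is not forbidden. Section 1.3 speaks of correlation, and Section 13 allows exploratory changes to be listed and explained in the study report. True, but the table names no such analysis, and one decided after outcomes are known carries less weight.

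**Conclusion.** The point holds as a cheap improvement to an exploratory analysis. Table 13.1 summarises outcomes by marker category with no cut points and no later SAP, while the hypothesis concerns levels and at least PD-L1 is quantitated.

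For a normal marker a median split keeps about 64% of the information. At n = 50 this corresponds to about 9 to 15 points of power under assumed shifts of 0.6 to 1.0 SD, ORR of 25% to 50%, a median split and a two-sided 5% chi-square. Weaker effects lose less and more extreme splits lose more.

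A reader should not infer that a stated power is missed, that every listed marker is better kept continuous, or that cuts have been chosen from the data. The documents show none of these. The primary ORR analysis and the secondary PFS, DOR and OS analyses are untouched.

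**What to change.** Amend the two exploratory rows of Table 13.1 as follows.

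- **Graded markers** (PD-1 and PD-L1 expression, ELISpot response, and CD3 and CD8 if their scores are graded): make a full-scale estimate with 95% CI the main summary. For ORR, show the marker's distribution in responders and non-responders with an odds ratio per SD or per doubling. For PFS and OS, give a Cox hazard ratio per SD.
- **Categories:** keep them for tables and Kaplan-Meier plots, with the cut fixed in advance, for example the median.
- **MCPyV serology:** analyse as positive or negative first, with titer among positives as a supplement. Keep truly binary markers binary.
- **Labelling:** mark all of these as exploratory and unadjusted for multiplicity.

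The cost is a few lines of text and some extra model fits on data already being collected. The downsides are an assumption of a monotone, log-linear relation, which the retained category displays can check, and wide intervals: at ORR 25% there would be only about 50 × 0.25 ≈ 12 responders.

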13.8 Stratification Factors- N/A

13.9 Interim Analyses

There will be one interim analysis at the end of Stage 1, on the first 9 patients ([Section 13.8](#)). If there are no responses in these 9 patients, the study will be stopped. Otherwise, 15 additional patients will be accrued for a total of 24.

13.10 Compliance (Medication Adherence)

Drug accountability data for trial treatment will be collected during the study. Compliance with trial treatment administration will be measured by subjects: (1) receiving unscheduled study agent infusions/injections; (2) missing an infusion/injection. Numbers and percentages of subjects and infusion/injection visits with any deviation in these measures will be reported for the eligible subjects

13.11 Extent of Exposure

The extent of exposure will be summarized as duration of treatment in cycles. Dose intensity will also be summarized as appropriate.

13.12 Analysis of Secondary Endpoints

Analysis of secondary endpoints is addressed in Section 13.6.1.

13.13 Reporting and Exclusions

13.13.1 Evaluation of Toxicity

All patients will be evaluable for toxicity from the time of their first treatment with MK-

3475.

13.13.2 *Evaluation of Response*

All patients included in the study must be assessed for response to treatment, even if there are major protocol treatment deviations or if they are ineligible. Each patient will be assigned one of the following categories: (1) CR, (2) PR, (3) SD, (4) PD, (5) early death from malignant disease, (6) early death from toxicity, (7) early death because of other cause, or (9) unknown (not assessable, insufficient data).

Note: By arbitrary convention, category 9 usually designates the “unknown” status of any type of data in a clinical database.

All of the patients who met the eligibility criteria (with the exception of those who received no study medication) should be included in the main analysis of the response rate. Patients in response categories 4–9 should be considered to have a treatment failure (disease progression). Thus, an incorrect treatment schedule or drug administration does not result in exclusion from the analysis of the response rate. Precise definitions for categories 4–9 will be protocol specific.

All conclusions should be based on all eligible patients. Subanalyses may then be performed on the basis of a subset of patients, excluding those for whom major protocol deviations have been identified (e.g., early death due to other reasons, early discontinuation of treatment, major protocol violations, etc.). However, these subanalyses may not serve as the basis for drawing conclusions concerning treatment efficacy, and the reasons for excluding patients from the analysis should be clearly reported. The 95% confidence intervals should also be provided.

REFERENCES

APPENDIX A PERFORMANCE STATUS CRITERIA

ECOG Performance Status Scale		Karnofsky Performance Scale	
Grade	Descriptions	Percent	Description
0	Normal activity. Fully active, able to carry on all pre-disease performance without restriction.	100	Normal, no complaints, no evidence of disease.
		90	Able to carry on normal activity; minor signs or symptoms of disease.
1	Symptoms, but ambulatory. Restricted in physically strenuous activity, but ambulatory and able to carry out work of a light or sedentary nature (e.g., light housework, office work).	80	Normal activity with effort; some signs or symptoms of disease.
		70	Cares for self, unable to carry on normal activity or to do active work.
2	In bed <50% of the time. Ambulatory and capable of all self-care, but unable to carry out any work activities. Up and about more than 50% of waking hours.	60	Requires occasional assistance, but is able to care for most of his/her needs.
		50	Requires considerable assistance and frequent medical care.
3	In bed >50% of the time. Capable of only limited self-care, confined to bed or chair more than 50% of waking hours.	40	Disabled, requires special care and assistance.
		30	Severely disabled, hospitalization indicated. Death not imminent.
4	100% bedridden. Completely disabled. Cannot carry on any self-care. Totally confined to bed or chair.	20	Very sick, hospitalization indicated. Death not imminent.
		10	Moribund, fatal processes progressing rapidly.
5	Dead.	0	Dead.

